2. TID PT
3. NO CPM
4. Jordan Splint: NO ORDER FOR JORDAN SPLINT
5. Cryotherapy: ICE BAGS ONLY
6. TED stockings FOR HOME USE
7. VENO DYNES for INHOUSE
8. NO DRAINS
9. Negotiate stairs with one rail + cane or two rails.
10. Patients can be cleared when independent on a walker OR cane.

Straight leg test (SLR):

- Tested with patient in supine with non-operated leg in knee flexion, patient is asked to perform a quad set (isometric quadriceps contraction) and while maintaining the contraction simultaneously lift operated left straight up to 45 degrees (hip flexion) or ~ six inches from the floor/bed.
- Test is considered to be positive if patient is able to perform SLR without extension lag (leg below knee unable to hold while performing SLR).
- Negative SLR is indicative of poor quadriceps control.

Research Staff:

Print: 2014-018 - The Combination of Adductor Canal Block and Periarticular Injectio...

Page 16 of 37

<https://ecap.hss.edu/eCAP/ResourceAdministration/Project/PrintSmartForms?Project=com.w...> 8/22/16

ID: 2014-018 Section: PART II - Clinical Research Proposal - Interventions or Observations

- 1) DOS, upon spinal resolution: NRS pain scores, painOUT
- 2) POD 1, 24-h post-anesthesia end: NRS pain scores, painOUT, Hospital DC lag questionnaire
- 3) POD 2, 48-h post-anesthesia end: NRS pain scores, painOUT, Hospital DC lag questionnaire

2.0 Will you be collecting human fluid or tissue? Yes No

If yes, what will you be collecting? Fluid Tissue

(Intraoperative and/or outpatient collection)

[Help](#)

[Help](#)

## Data Collection

1.0 Indicate what data will be collected.

Data will be collected by a research staff member or a co-investigator. Please see the data collection sheets for further detail.

1. Day of Surgery in the holding area - patient demographics (name, age, sex, race, BMI); NRS pain score at rest, during ambulation, while bending knee
2. Day of Surgery upon spinal resolution - Procedure length; ASA classification; tourniquet time; NRS pain score at rest, during ambulation, while bending knee; painOUT; opioid consumption; PT data sheet (assessing lines, nausea, vomiting, dizziness, pain NRS post-PT, buckling, transfer details, ambulation details, stair details, straight leg raise)
3. POD 1 - NRS pain score at rest, during ambulation, while bending knee; painOUT; opioid consumption; PT data in the morning, afternoon, and evening (assessing lines, nausea, vomiting, dizziness, pain NRS post-PT, buckling, transfer details, ambulation details, stair details, straight leg raise; was discharge criteria met (time and date)?); Hospital DC lag questionnaire
4. POD 2 - NRS pain score at rest, during ambulation, while bending knee; painOUT; opioid consumption; PT data in the morning, afternoon, and evening (assessing lines, nausea, vomiting, dizziness, pain NRS post-PT, buckling, transfer details, ambulation details, stair details, straight leg raise; was discharge criteria met (time and date)?); Hospital DC lag questionnaire
5. Knee Society Score - Both pre-operatively and at first post operative surgeon's office visit (obtained through Total Joint Registry)

2.0 Who will collect the data:

[name].

[name], PhD IRB Vice Chair

Print: 2014-018 - The Combination of Adductor Canal Block and Periarticular Injectio...

Page 17 of 37

<https://ecap.hss.edu/eCAP/ResourceAdministration/Project/PrintSmartForms?Project=com.w...> 8/22/16

ID: 2014-018 Section: PART II - Clinical Research Proposal - Interventions or Observations

[name] Research Assistant

[name] Physical Therapist

[name]

[name]

[name]

[name]

[name] Assistant Director, Research

[name]

[name] Physical Therapist

[name] Research Associate

[name]

[name]

[name]

[name] Regional Anesthesia fellow

3.0 When the data will be collected? Include timing of visits(either

SOC or specifically for the study).

During the patients' hospital stay and visits to surgeons offices

4.0

From what source:

Medical Records

Patient

No Private Office Charts Please specify which private office:

Yes Registries Please specify which registry: Total Joint

Other Please specify:

Help

Help

## Surveys & Questionnaires

1.0 Please add all survey instruments and questionnaires to be used in this study:

Name

Standard

Instrument

Upload Instrument Usage of Instrument

[View painOUTyes](#)

[painOUT](#)

[Questionnaire\(0.01\)](#)

This instrument will be used to acquire secondary outcome data.

[Help](#)

## Randomization

1.0 Please state who will do the Randomization:

A research assistant not otherwise involved with the study will prepare a randomization table. Group assignment will be indicated on cards within numbered sealed opaque envelopes. After consent is obtained, the envelope will be opened in the operating room, not in the presence of the investigators who plan to assess the patients postoperatively.

Print: 2014-018 - The Combination of Adductor Canal Block and Periarticular Injectio...

Page 19 of 37

<https://ecap.hss.edu/eCAP/ResourceAdministration/Project/PrintSmartForms?Project=cm.w...> 8/22/16

ID: 2014-018 Section: PART II - Clinical Research Proposal - Interventions or Observations

2.0 Please state when the Randomization will be done:

The randomization will occur once IRB approval has been obtained and prior to the start of study enrollment. Randomization has been generated via computer randomizer. Randomization will be revealed after the patient gives consent and it is obtained in the holding area prior to surgery. At the time consent is obtained the anesthesiologist will be given a sealed opaque envelope corresponding to the patients study id number and randomization to either treatment or control.

3.0 Please state how the Randomization will be performed:

A research assistant not otherwise involved with the study will prepare a randomization table using randomizer software.

4.0 Please state who will insure that the Randomization is carried out and if anyone will be blinded to the Randomization group:

The Research Manager will ensure that the randomization is carried out. The physical therapist, nursing, PA, pain team, research staff, as well as the study patient will be unaware of which interventional group the study patient is in.

[Help](#)

ID: 2014-018 Section: PART II - Clinical Research Proposal - Sample Size & Data Analysis

[Help](#)

## Sample Size and Data Analysis

If you are uncertain about how to calculate your sample size and determine appropriate data analysis, please contact the Epidemiology and Biostatistics Core at [[contact]](mailto:[contact])

for assistance in completing this section.

1.0

Is this is a case series based only on the patients available using descriptive statistics in lieu of a sample size calculation?

\* No

Help

Help

## Sample Size and Data Analysis

Support estimates with evidence from the literature of prior studies and perform an appropriate sample size calculation.

Print: 2014-018 - The Combination of Adductor Canal Block and Periarticular Injectio...

Page 20 of 37

<https://ecap.hss.edu/eCAP/ResourceAdministration/Project/PrintSmartForms?Project=cm.w...> 8/22/16

ID: 2014-018 Section: PART II - Clinical Research Proposal - Sample Size & Data Analysis

For hypothesis testing (e.g., the calculation of p-values using statistical tests), you need to

estimate your available sample size and calculate the effect size that will be detectable using your proposed statistical analysis plan. This also applies to a case series where you

plan hypothesis testing.

1.0 If you have consulted with a statistician, please indicate their name:

[name]

2.0 Proposed sample size analysis, include the following:

- Student's t-test, ANOVA, chi-square, regression, etc;
- Alpha level;
- Beta or power level;
- Primary outcome variable estimate (mean +/-s.d. for continuous outcome, frequency/percentage for categorical variable);
- Number of groups being compared (use 1 for paired analysis within the same subjects);
- Effect size or change expected between groups;
- Resulting number per group

A previous trial at HSS found the standard deviation (SD) in time until ready for discharge (based on achievement of PCA, nausea, diet, urination, pain, surgical, medical, and PT criteria) for TKR patients receiving periarticular injections to be 0.83 days (YaDeau, 2013). This SD was considered to be a reasonable estimate of the variability in the time until patient is able to independently negotiate stairs within the periarticular injection alone group. A 0.5 day difference in mean time until patient is able to independently negotiate stairs between the periarticular injection alone and periarticular injection + ACB groups was determined to be clinically meaningful. With two-sided alpha set at 0.05, power at 0.8, and the addition of 10% more patients to account for potential protocol violations, the number of patients required for a two-sample t-test is 53 patients per group (106 patients total\*).

\*Our a priori sample size calculation assumed that 96 of 106 enrolled patients would adhere to trial protocol. However, ultimately only 92 out of 106 patients adhered to trial protocol. Therefore, we plan to continue enrollment up to 114

patients until 96 patients without protocol deviations are enrolled.

3.0

**Data Analysis:** describe how the primary outcome will be analyzed and what types of statistical calculations will be used. Do the same for each secondary outcome. Reiterate briefly the main analysis to be done, which groups, which variables, possible confounders. Address how possible confounders will be identified and handled in analysis:

Print: 2014-018 - The Combination of Adductor Canal Block and Periarticular Injectio...

Page 21 of 37

<https://ecap.hss.edu/eCAP/ResourceAdministration/Project/PrintSmartForms?Project=cm.w...> 8/22/16

ID: 2014-018 Section: PART II - Clinical Research Proposal - Sample Size & Data Analysis

The primary outcome, time until the patient is able to independently negotiate stairs, will be compared between the periarticular injection alone and periarticular injection + ACB groups with a two-sample t-test or Wilcoxon rank-sum test, depending upon the distribution of the data. The precision of the estimate of the difference between groups will either be reported as a 95% confidence interval for the difference in means or the Hodges-Lehmann estimate of location shift. Longitudinal secondary outcome data (NRS pain scores, narcotic consumption, incidence of side effects, painOUT score, and patient satisfaction) will be compared between groups via the generalized estimating equations (GEE) approach.

Change in KSS, and hospital length of stay will be compared between groups with two-sample t-tests or Wilcoxon rank-sum tests, depending upon the distribution of the data.

The success of blinding in each arm will be assessed with the Bang Blinding Index' (Bang H, Flaherty SP, Kolahi J, Park J. Blinding assessment in clinical trials: A review of statistical methods and a proposal of blinding assessment protocol. *Clin Res Regul Aff* 2010; 27:42-51.)

[Help](#)

[Help](#)

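### The 53 per group and the 96 adherent patients do not follow from the stated t-test inputs, which give 45 evaluable and 49 to 50 enrolled per group if SD 0.83 d holds in both arms

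*Combined protocol and SAP*

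**What the plan says.** In the combined protocol and SAP, Sample Size and Data Analysis, item 2.0, the SD of 0.83 days comes from a previous trial at the same hospital. The endpoint there was "time until ready for discharge (based on achievement of PCA, nausea, diet, urination, pain, surgical, medical, and PT criteria"), in patients given periarticular injections. The plan takes this SD as a reasonable estimate for the time "until patient is able to independently negotiate stairs within the periarticular injection alone group". It gives no SD for the ACB arm. A difference of 0.5 day in mean time is called clinically meaningful.

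The calculation is then stated as follows: "With two-sided alpha set at 0.05, power at 0.8, and the addition of 10% more patients" for protocol violations, "the number of patients required for a two-sample t-test is 53 patients per group", or 106 in total.

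A footnote to the same item says: "Our a priori sample size calculation assumed that 96 of 106 enrolled patients would adhere to trial protocol". It continues: "However, ultimately only 92 out of 106 patients adhered to trial protocol". Enrolment is therefore to go on up to 114 "patients until 96 patients without protocol deviations are enrolled". The HSS Clinical Trial section, item 6.0, repeats the 114 and the 96 and says that half of the patients receive the block.

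Item 3.0 (Data Analysis) compares the primary outcome between the "groups with a two-sample t-test or Wilcoxon rank-sum test, depending upon the distribution of the data". Item 2.0 mentions only the t-test and no allowance for a rank-based analysis.

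**The concern.** Item 2.0 lists a test, alpha, power, SD, difference and inflation, and presents 53 per group as the result. A reader who enters those inputs in a standard calculation gets a smaller number, and neither rounding nor the way in which the 10% is applied closes the gap.

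The figure is in active use. The 96 adherent patients are the target that keeps enrolment open beyond 106. Whether four more adherent patients are needed to hold 80% power depends on what the 96 rests on, and the text does not say.

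**Working it through.** **Inputs** (item 2.0 unless noted): SD 0.83 d, stated for the periarticular-alone arm; difference 0.5 d; two-sided alpha 0.05; power 0.80; 10% added; two-sample t-test; equal allocation (HSS Clinical Trial, item 6.0). A common SD of 0.83 d in both arms is my assumption.

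**1. The plan's own figures.** A base of 48 per group fits them: 48 × 1.1 = 52.8, so 53; 2 × 48 = 96; 96 × 1.1 = 105.6, so 106. The document never states 48, however. A base of 47 with division also reaches 53 (47 / 0.9 = 52.2), and 96 could have been worked back from 106 (106 × 0.9 = 95.4, so 96). The wording about adding 10% favours multiplication, so 48 is the more natural inference, but it remains an inference.

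**2. Required n from the stated inputs.**
- Normal approximation: 2 × (1.960 + 0.842)² × 0.83² / 0.5² = 43.26, so 44 per group.
- Exact t-test: noncentrality 0.5 / (0.83 × √(2/n)) with 2n − 2 degrees of freedom. The solution is n = 44.24, so 45 per group, or 90 in total. Power is 79.8% at 44 and 80.7% at 45.
- With 10% added: 44.24 × 1.1 = 48.7, so 49; 45 × 1.1 = 49.5, so 50; 45 / 0.9 = 50. That is 98 to 100 in total.
- Against an inferred base of 48, the gap is 3 evaluable per group (6 in total). Against the stated 53, it is 3 to 4 enrolled per group (6 to 8 in total).
- Other design settings do not give 48: one-sided alpha needs 35 per group, power 0.85 needs 51 and power 0.90 needs 59.

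**3. Power at the sizes in play, SD 0.83 d in both arms.** The rank-sum column uses an effective n of n × 3/π.

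| n per group | t-test | 3/π rank-sum allowance |
|---|---|---|
| 45 (90) | 80.7% | not computed |
| 46 (92) | 81.5% | 79.7% |
| 48 (96) | 83.2% | 81.4% |
| 53 (106) | 86.7% | 85.1% |

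With 92 patients and equal SDs, t-test power stays at or above 80% for splits no worse than 37/55 (80.0%); at 36/56 it is 79.7%.

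**4. Unstated inputs that would give 48.**
- A 3/π rank-sum allowance on the rounded 45: 45 × π/3 = 47.1, so 48. On the unrounded 44.24 it gives 46.3, so 47.
- An ACB-arm SD of about 0.882 to 0.899 d, with 0.83 d in the other arm.
- A common SD of about 0.86 d.
- A difference of about 0.48 d.

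**5. Dependence on the ACB-arm SD.** With unequal SDs, I replace 0.83 by √((0.83² + s²)/2), where s is the ACB-arm SD. At 48 per group:

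| ACB-arm SD | Power |
|---|---|
| 0.70 d | 88.4% |
| 0.83 d | 83.2% |
| 0.90 d | 80.0% |
| 1.00 d | 75.1% |

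At 46 per group, power falls below 80% once the ACB-arm SD exceeds about 0.863 d.

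**The case against.** The strongest reply is that the inputs are incomplete rather than contradictory. No ACB-arm SD is given, so the stated inputs do not fix a single n, and a modestly larger SD in that arm yields exactly 48. In addition, item 3.0 allows the rank-sum test. The primary outcome is read only at scheduled therapy sessions (Specific Aims, item 4.0), so some headroom over the t-test minimum is sensible design. A 3/π allowance on 45 leads to 48 and then 53.

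Much of this stands. It makes the figures plausible, and it shows that the defect lies in the documented derivation. It does not make the sentence in item 2.0 correct. That sentence attributes 53 to a two-sample t-test and gives one SD, with no rank-sum factor and no second SD. Several routes reach 48, and the text does not show which was used, if any.

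A second reply is that little follows in practice: the gap is small beside the uncertainty of an SD borrowed from a composite discharge-readiness endpoint. That also stands, and it is why the point is minor.

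A reader might infer that the extension beyond 106 was unnecessary, because 92 adherent patients already exceed 80% power. The documents do not support this. The 81.5% needs equal SDs, a near-even split and a t-test analysis. Under a 3/π allowance 92 patients give 79.7%, and an ACB-arm SD above about 0.863 d also takes them below 80%.

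**Conclusion.** The point holds as a minor one. The stated 53 per group and 96 adherent do not follow from the stated t-test inputs. With SD 0.83 d assumed in both arms, those inputs give 45 evaluable and 49 to 50 enrolled per group. The base of 48 is inferred, and its origin cannot be established from the text.

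A reader might also conclude that the gap is harmless because it can only add power. That is conditional. At 48 per group the design keeps 80% power only if the ACB-arm SD is no more than about 0.90 d, and the documents give no SD for that arm. Nor do they show the trial to be underpowered: on its own inputs with equal SDs, 96 evaluable patients give 83.2%. The discrepancy in the sample size arithmetic has no effect on alpha.

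**What to change.** In Sample Size and Data Analysis, item 2.0, correct the statement that 53 per group is what the t-test requires for 80% power. Keep 53, 106 and 96 as the a priori figures, keep the report that 92 of 106 adhered, and add one of the following:

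- **Power delivered:** state that SD 0.83 d is assumed in both arms and that the t-test then has 83% power at 96 evaluable patients and 87% at 106.
- **Basis actually used:** give the ACB-arm SD or the rank-sum factor behind the figure, with the resulting power (about 81% at 96 under a 3/π factor).

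Then rest the target of 96 and the extension to 114 on that stated basis. The cost is one or two sentences, with no change to patient numbers, data collection or analysis.

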A spinal anesthetic with 0.5% bupivacaine (10 or 12.5) will be performed. Then the adductor canal block\* technique will be performed; supine position, after IV sedation. Ultrasound guided with linear transducer 8 MHz. Chiba needle, 22 G / 4 inches. The femoral artery will be identified in the adductor canal deep to the Sartorius muscle. The block will consist of 15 cc of Bupivacaine 0.25% with 2 mg of Preservative free Dexamethasone. The local anesthetic will be delivered periarterial between 12 and 6 o'clock. The surgeon will perform the periarticular injections; one deep injection prior to cementation and then a second more superficial injection prior to closure. The deep injection will consist of bupivacaine 0.5% with epinephrine, 30cc; morphine, 8 mg/ml, 1 cc; methylprednisolone, 40 mg/ml, 1 ml; cefazolin, 500 mg in 10 ml; normal saline, 22cc. The superficial injection will be 20 ml 0.25% bupivacaine. Patients will not be given intravenous opioids or ketamine during the operation. Patients will be given 4 mg Ondansetron and 20 mg Famotidine.

\*The block function will be assessed and recorded by the Anesthesiologist postoperatively.

The assessment of the adductor canal block will be done in the

Recovery room after the resolution of the spinal anesthesia. We will use a alcohol swab to test the cold sensation first on the non operated leg and then on the operated one. The test will be performed at the level of the medial maleoli of

the tibia. If the patient has sensation or no sensation it will be recorded as Block NOT working or Block working, respectively. The same procedures will be followed for the peri-articular injection only group, so as to not unblind participating patients.

Postoperative:

Print: 2014-018 - The Combination of Adductor Canal Block and Periarticular Injectio...

Page 15 of 37

<https://ecap.hss.edu/eCAP/ResourceAdministration/Project/PrintSmartForms?Project=cm.w...> 8/22/16

ID: 2014-018 Section: PART II - Clinical Research Proposal - Interventions or Observations

Analgesia:

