## Consent Information

1.0 Describe how, when, and where the consent process will be initiated:

A MD co-investigator will obtain consent from the patient in the holding area prior to entering the operating room on the day of surgery. That physician will also serve as that patient's anesthesiologist.

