2.0 PI: [[name].](#)

3.0 Co-Investigators:

First Name Middle Name Last Name Title

[name], PhD IRB Vice Chair

[name] Research Assistant

[name]

[name]

[name] Volunteer

[name]

[name] Physical Therapist

[name]

[name]

[name]. MD

[name]

[name]

[name]

[name] Assistant Director, Research

[name]

[name] Physical Therapist

[name] Research Associate

[name]

[name]

[name]

[name]

[name] Regional Anesthesia fellow

4.0

Posting date:

Print: 2014-018 - The Combination of Adductor Canal Block and Periarticular Injectio...

Page 36 of 37

<https://ecap.hss.edu/eCAP/ResourceAdministration/Project/PrintSmartForms?Project=comb...> 8/22/16

ID: 2014-018 Section: HSS Clinical Trial Registry

Name

Upon IRB approval

Post on this date:

5.0

Condition:

Arthroplasty

Other:

6.0 State the summary including number of patients, enrollment period and duration of follow-up (use lay terms):

We plan to enroll up to 114 patients undergoing knee replacement in order to get 96 patients with usable data. All patients will receive peri articular injections as an anesthetic regimen. Half will additionally receive an adductor canal block.

Patients will also have an accelerated physical therapy protocol to aid the achievement of rehab milestones. The primary outcome is time when patient is able to meet physical therapy discharge criteria, indicated by the ability to independently negotiate stairs- non-reciprocal (one leg at a time), with or without rails, and with or without assistive device (walker or cane).

7.0 State the inclusion and exclusion criteria (use lay terms):

8.0 State the contact information for the study:

[Help](#)

Print: 2014-018 - The Combination of Adductor Canal Block and Periarticular Injectio...

Page 37 of 37

<https://ecap.hss.edu/eCAP/ResourceAdministration/Project/PrintSmartForms?Project=comb...>

8/22/16

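### No primary analysis population is named, and the rule for extending enrolment points to, without stating, a comparison of deviation-free patients only

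*Combined protocol and SAP*

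**What the plan says.** All references are to the combined protocol and SAP.

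- **Sample Size and Data Analysis, 2.0.** The calculation includes "the addition of 10% more patients to account for potential protocol violations" and arrives at 53 per group, 106 in total. The footnote says 96 of the 106 were expected to adhere, and then: "However, ultimately only 92 out of 106 patients adhered to trial protocol". Enrolment is therefore to continue, to at most 114 "patients until 96 patients without protocol deviations are enrolled".
- **Sample Size and Data Analysis, 3.0.** The primary outcome is compared between the two arms by t-test or Wilcoxon rank-sum test. No intention-to-treat, modified or per-protocol set is named, and there is no rule for patients with deviations.
- **HSS Clinical Trial, 6.0.** The lay summary gives the purpose of enrolling up to 114 as "in order to get 96 patients with usable data".
- **Randomization, 2.0 and 4.0.** "At the time consent is obtained the anesthesiologist will be given a sealed opaque envelope". The list of those kept unaware covers the therapist, nursing, PA, pain team, research staff and patient. It does not include the anesthesiologist.
- **Consent Information, 1.0.** Of the co-investigator who takes consent: "That physician will also serve as that patient's anesthesiologist".
- **Data Safety Monitoring Plan, 2.0.** Patients with complications are withdrawn. Nothing is said about their outcome data or their place in the analysis.

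**The concern.** Without a named set, the primary test is not fully defined. The deviation-free patients (92 now, 96 at the target) and the randomised patients (106 now, up to 114) give two different tests of the same hypothesis.

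The enrolment rule leans towards the first. It replaces non-adherent patients until a count of adherent ones is reached, and the registry summary equates that count with usable data. If the plan were followed in that sense, about one randomised patient in seven would be dropped on the basis of something that happened after allocation.

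That is harmless only if exclusion does not depend jointly on arm and prognosis. The arms have different steps to deviate from, since the block exists in one arm only, and the anesthesiologist receives the allocation. The opportunity for arm-dependent exclusion therefore exists. The footnote gives neither the arms of, nor the reasons for, the 14 deviations, so a reader cannot tell whether it was realised.

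**Working it through.** **Inputs** (Sample Size and Data Analysis, 2.0): SD 0.83 d, difference 0.5 d, two-sided alpha 0.05, power 0.80, 10% added; 53 per group; 96 of 106 expected to adhere, 92 of 106 observed; cap 114, target 96.

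**The plan's own figure.** The two-sample t-test needs 44.2, so 45 per arm. Adding 10% gives 45 × 1.10 = 49.5, so 50 per arm, not 53. The stated 96 adherent patients are 48 per arm, and 48 × 1.10 = 52.8, which rounds to 53. The step from 96 to 106 therefore matches the 10%, while 48 per arm is more than the stated inputs require. This errs on the safe side and does not affect the present point.

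**Patients at stake.**
- Planned: 106 − 96 = 10, and 10/106 = 9.4%.
- Now: 106 − 92 = 14, and 14/106 = 13.2%.
- At the cap: 114 − 96 = 18, and 18/114 = 15.8%.

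**Power with the full 0.5 d effect** (noncentral t, equal arms):

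| Set | Per arm | Power |
|---|---|---|
| Deviation-free, 92 | 46 | 81.5% |
| Deviation-free, 96 | 48 | 83.2% |
| All randomised, 106 | 53 | 86.7% |
| All randomised, 114 | 57 | 89.0% |

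**Power for all randomised patients if non-adherent patients show no effect.** The difference shrinks to 0.5 × (adherent block-arm patients ÷ block-arm total). How deviations split by arm is an assumption, because the documents do not give it.

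| Randomised | Deviations, block/control | Difference | Power |
|---|---|---|---|
| 106 | 7/7 | 0.5 × 46/53 = 0.434 d | 76.0% |
| 106 | 10/4 | 0.5 × 43/53 = 0.406 d | 70.3% |
| 114 | 9/9 | 0.5 × 48/57 = 0.421 d | 76.6% |
| 114 | 13/5 | 0.5 × 44/57 = 0.386 d | 69.2% |

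With an even split, 80% power needs a difference of 0.456 d (106) or 0.439 d (114). Non-adherent patients must then keep (0.456 − 0.434)/(0.5 × 0.132) = 33% of the effect, or (0.439 − 0.421)/(0.5 × 0.158) = 23%.

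**Error rates, as illustrations only.**
- *Better of two tests, no selection bias.* The two statistics correlate at √(92/106) = 0.932 or √(96/114) = 0.918. The chance that at least one is significant under no effect is 6.7% or 6.9%. The plan does not say both would be run and one chosen.
- *Arm-dependent exclusion.* Assume no true effect, 10 slower patients per arm, and 10 slow block and 4 slow control patients excluded. Six slow patients remain among 49 controls. If they are 0.83 d slower, the shift is 6/49 × 0.83 = 0.10 d, with a simulated type I error of 8.0–8.6%. If 0.415 d slower, the shift is 0.05 d and the error 5.7–5.9%.
- *Exclusion unrelated to arm.* The shift is 0 d and the error 4.9–5.0%. When the split happens by chance to be 10/4, the shift stays below 0.004 d and the error is 4.7–5.1%.

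**The case against.** The strongest reply is that nothing here is a demonstrated error. The analysis text compares the two groups, and Randomization 1.0 defines group by the assignment card, so analysing everyone as assigned is a natural reading. Adding patients for violations may simply protect power against dilution. Therapists, ward and research staff and patients are blinded, which limits arm-dependent deviations after surgery. All of this stands, and it is why the point is not a blocking one. It does not supply the missing sentence, and the registry wording on usable data pulls the other way.

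A reader might infer more than the documents support in four places:

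- *That non-adherent patients will be excluded.* No passage says so.
- *That the result is biased or the error rate inflated.* The figures above 5% need assumed splits, assumed slowness or after-the-fact choice of test, none of which is documented. An uneven split by chance alone causes no bias.
- *That a failed block counts as a deviation.* The cold test result is noted ("it will be recorded as Block NOT working or Block working, respectively"), but the same procedure is followed in the injection-only group and no text links it to deviation status.
- *That the time of randomisation is contradictory.* A list prepared in advance, an envelope handed over at consent, and then "the envelope will be opened in the operating room" can be read as one sequence.

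Two objections to the remedy also stand. The 76.0% and 76.6% powers are not a floor, because they assume an even split; the 10/4 and 13/5 rows show lower values. Nor can stairs times for non-adherent patients be taken as available. General Methods and Procedures 1.1 promises identical data in answer to a question about controls, not deviators. Data Collection 1.0 lists the time of meeting discharge criteria only for POD 1 and POD 2, although Specific Aims 4.0 describes daily assessment afterwards.

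Finally, General Methods and Procedures 7.0 lists an anesthesiologist checklist and another uploaded data collection file that are not reproduced. The absence of a deviation definition is established only for the text at hand.

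**Conclusion.** The point holds as a gap that should be fixed. The primary analysis population is not named, and the enrolment rule together with the registry summary points to, without stating, a deviation-free comparison. At stake are 14 of 106 patients (13.2%) now and up to 18 of 114 (15.8%) at the cap, removed after randomisation. The counts follow directly from the footnote. The powers rest on the plan's SD of 0.83 d and difference of 0.5 d. The diluted powers also rest on assumed arm splits and no effect in non-adherent patients. Selection bias remains a possibility that the design leaves open, and the error rates above 5% only illustrate what it could do.

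**What to change.** 1. In Sample Size and Data Analysis 3.0, state that the primary analysis includes every randomised patient in the assigned group.
2. Keep the deviation-free set as a sensitivity analysis, and say what counts as a deviation so that this set is reproducible.
3. Report deviations by arm, with reasons.
4. Align the usable-data wording in HSS Clinical Trial 6.0 with the named set.
5. Confirm that stairs times are collected for patients with deviations and for those withdrawn under Data Safety Monitoring Plan 2.0, since the documents do not say so expressly.

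Items 1 to 4 are mainly wording. Item 5 may show missing times, which would then need a stated handling rule. The statistical cost is dilution, as tabulated in the working: power stays above 80% if non-adherent patients keep a fair part of the effect, and could fall to about 70% (106) or 69% (114) if they show none and deviations concentrate in the block arm.
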